6.3 DEMOGRAPHICS AND BASELINE CHARACTERISTICS

The following summaries will be presented:

- Demographics
 - Age (years) at enrollment
 - Sex
 - Childbearing potential for female: fertile/non-fertile. Reason if non-fertile.
 - Ethnicity
 - Race
- Baseline Characteristics
 - Height, weight and BMI
 - ECOG status

Demographics and baseline characteristics will be listed by subject.

6.4 PRIMARY TUMOR DIAGNOSIS

Primary tumor diagnosis will be listed by subject.

6.5 GENERAL MEDICAL HISTORY

Medical history events will be coded to system organ class (SOC) and preferred term (PT) using the Medical Dictionary for Regulatory Activities (MedDRA) version 25.1. The number and percentage of subjects who experienced at least one medical history event will be summarized by SOC and PT. A subject who had multiple medical history events in a SOC/PT category will only be counted once for that category.

6.6 PRIOR SYSTEMIC THERAPY

Prior systemic therapies will be listed by subject.

6.7 PRIOR RADIOTHERAPY

Prior radiotherapies will be listed by subject.

6.8 PRIOR SURGICAL/PROCEDURE THERAPY

Prior surgical/procedure therapies will be listed by subject.

6.9 PRIOR AND CONCOMITANT MEDICATIONS

All medications collected on the CRF page ‘Prior and Concomitant Medications’ will be coded to the anatomical therapeutic chemical (ATC) level 3 and preferred name using the WHO Drug Dictionary Global B3 format of September 2022 release. The number and percentage of subjects who had at least one prior or concomitant medication will be summarized by ATC level 3 and preferred name. A subject who had multiple prior or concomitant medications in an ATC level 3/preferred name category will only be counted once for that category.

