### Parameters to be Assessed/Endpoints:

#### Part 1

**Efficacy:** Anti-tumor activity of the combination of TJ004309 and atezolizumab will be measured by best of response (BOR), objective response rate (ORR), duration of response (DoR), disease control rate (DCR), progression free survival (PFS) and overall survival (OS) based on RECIST 1.1 and iRECIST.

**Safety:** Treatment-emergent AEs (including serious AEs and immune-related AEs) evaluated using the National Cancer Institute Common Terminology Criteria for Adverse Events (CTCAE) criteria (version 5.0), changes from baseline in clinical laboratory parameters (complete blood counts [CBC] and serum chemistry), 12-lead electrocardiograms (ECGs), vital sign measurements, physical examinations, ECOG performance status, and use of concomitant medications.

**Pharmacokinetics:** Serum TJ004309 concentration will be measured using validated methods at the time points specified in the Schedule of Assessments to determine PK parameters including  $C_{max}$  and  $C_{trough}$ .

**Immunogenicity:** TJ004309 anti-drug antibodies (ADA) will be measured using validated methods at time points specified in the Schedule of Events.

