## 6.8 Concomitant Therapy

All prescription and non-prescription medications and therapies, including pharmacologic doses of vitamins, herbal medicines, or other non-traditional medicines, taken from 28 days prior to the first study drug dose are to be documented as *prior* medications. Medications taken from the time of the first study drug dose on C1D1 through 30 days after the last study drug dose are to be recorded as *concomitant* medications in the electronic case report form (eCRF). All therapies for primary diagnosis should be recorded regardless of when they were taken.

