### 9.2.5 Safety Analyses

All safety analyses will be performed on the Safety Analysis Population. The safety assessment will be based on the frequency of AEs, on the observation of clinically significant abnormalities of laboratory values, concomitant medication use, vital signs, ECGs, ECOG performance status, and physical examination data in the Safety Analysis Population.

AEs will be coded using the standard Medical Dictionary for Regulatory Activities (MedDRA), Version 23.0 or higher. Adverse events will be graded by the Investigator according to the CTCAE, version 5.0.

Analyses of AEs will be based on the principle of treatment emergence. Treatment-emergent AEs are defined as having onset after study drug dosing or a sign, symptom, or diagnosis that worsens after study drug dosing. Henceforth, whenever an analysis or summary of AEs is mentioned, it is intended that this is in reference to treatment-emergent adverse events (TEAEs), unless it is stated otherwise.

TEAEs will be summarized based on the number and percentage of patients experiencing the event by system organ class (SOC) and preferred term (PT). The causal relationship between the occurrence of an AE and study drug will be judged by the Investigator on the basis of his or her clinical judgment (i.e., Related, Possibly Related, Probably Related, Unlikely Related, and Not Related). In the event a patient experiences repeat episodes of the same AE, then the event with the highest severity grade and strongest causal relationship to study drug will be used for purposes of incidence tabulations.

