9.1 ADVERSE EVENTS

Adverse events (AEs) will be coded to the system organ class (SOC) and preferred term (PT) using MedDRA version 25.1. Toxicity grading is based on the National Cancer Institute Common Terminology Criteria for Adverse Events (NCI CTCAE) version 5.0.

All AE summaries will be limited to the treatment-emergent adverse events (TEAEs). A TEAE is defined as an AE that has an onset or a worsening in severity during or after the first dose of study drug and up to 30 days after the last dose of study drug, or one day prior to the subsequent anti-tumor therapy, whichever occurs earlier. An AE that has a change in severity will be recorded as two separate AEs on the CRF under the same SOC/PT of different severity levels. If an AE has a missing onset date, it will be considered as a TEAE in the below situations:

- An AE whose onset date and end date are both missing.
- An AE where the onset date is missing and the end date is after the first dose date of study drug
- An AE where the onset date is missing, the end date is on the first dose date of study drug, and the end time (hh:mm) is absent or after the initiation of the first dose of study drug.

An overall summary of TEAEs will be presented to include the number and percentage of subjects with at least 1 TEAE in the following categories:

- Any TEAE
- Serious TEAE
- TEAE of CTCAE grade ≥ 3
- TEAE of maximum CTCAE Grade 3
- TEAE of maximum CTCAE Grade 4
- TEAE of maximum CTCAE Grade 5
- Infusion-related reaction
- TEAE related to any study drug
- TEAE related to TJ004309
- TEAE related to atezolizumab
- Serious TEAE related to any study drug
- Serious TEAE related to TJ004309

- Serious TEAE related to atezolizumab
- TEAE of CTCAE grade ≥ 3 related to any study drug
- TEAE of CTCAE grade ≥ 3 related to TJ004309
- TEAE of CTCAE grade ≥ 3 related to atezolizumab
- TEAE leading to any study drug discontinuation
- TEAE leading to TJ004309 discontinuation
- TEAE leading to atezolizumab discontinuation
- TEAE leading to death

In addition, the number and percentage of subjects with at least one TEAE in the following categories will be summarized by SOC and PT (unless noted otherwise below) for each cohort and overall:

- Any TEAE (summarized by SOC, PT and maximum CTCAE grade)
- Serious TEAE
- TEAE of CTCAE grade ≥ 3 (summarized by SOC, PT and maximum CTCAE grade)
- TEAE of CTCAE grade ≥ 3 related to any study drug (summarized by SOC, PT and maximum CTCAE grade)

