9.3 CLINICAL LABORATORY PARAMETERS

Hematology, chemistry, coagulation, thyroid function testing, CA125 test, dipstick urinalysis and microscopic laboratory results will be listed by visit per subject.

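### SAP 6.9 counts prior and concomitant medications together, so on-study use cannot be separated from pre-treatment use

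*SAP*

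**What the plan says.** Protocol 6.8 (Concomitant Therapy) sets two periods. The prior category holds drugs "taken from 28 days prior to the first study drug dose are to be documented as" such. The concomitant category has its own window and covers "Medications taken from the time of the first study drug dose on C1D1 through 30 days after the last study drug dose".

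The protocol then gives the second group a role in the safety evaluation. The Part 1 safety parameters in the synopsis end with "vital sign measurements, physical examinations, ECOG performance status, and use of concomitant medications". Section 9.2.5 bases the safety assessment on adverse events and on a set of data types that includes "clinically significant abnormalities of laboratory values, concomitant medication use, vital signs".

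SAP 6.9 takes all records from one CRF page, codes them, and reports the number and percentage of "subjects who had at least one prior or concomitant medication will be summarized by ATC level 3 and preferred name". The counting rule uses the same combined term: "A subject who had multiple prior or concomitant medications in an ATC level 3/preferred name category will only be counted once for that category". The section does not define the two periods and states no by-subject listing. Under SAP 4.1 and the opening of SAP section 6, the table is presented by cohort and overall in the safety analysis set.

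**The concern.** The protocol asks what patients took while on TJ004309 plus atezolizumab. The planned table shows what they took at any time from four weeks before first dose to 30 days after last dose.

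Systemic corticosteroids are the clearest case where the difference matters. Protocol 6.8.1 restricts them during treatment but allows acute use for suspected immune-related events. Table 7 permits them before later infusions after a Grade 2 infusion reaction, and Table 8 directs them for many immune-related events. In the Phase 1 study, 11 of 20 patients (55%) had a Grade 2 infusion reaction (protocol 4.3, Table 4). That is a reason to want on-study steroid use in view; it is not a forecast for this study. If steroids are recorded, the pooled row will not show whether they were taken before or during treatment.

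**Working it through.** The plan gives no figure to reproduce. The check is whether any stated output lets a reader recover on-study use.

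**1. What the counting rule keeps.** For one ATC level 3/preferred name category, let
- P = subjects with use only before first dose,
- C = subjects with use only from first dose onward,
- B = subjects with use in both periods.

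The SAP 6.9 table reports k = P + C + B. On-study use is C + B = k − P. The table does not report P, which can be anything from 0 to k. Hence 0 ≤ C + B ≤ k: the pooled count is an upper bound on on-study use, and the lower bound is zero.

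**2. Could the wording mean two tables?** The phrase in "subjects who had at least one prior or concomitant medication will be summarized by ATC level 3 and preferred name" might loosely be read that way. The counting rule makes this unlikely, because it collapses several records of either kind to one per category and names no period.

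**3. Can the split be recovered from a listing?** SAP 6.6 to 6.8 and 6.11 to 6.13 each state a by-subject listing for prior or subsequent anticancer therapy. SAP 6.9 states none for medications. SAP 4.1 says how listings are arranged, by cohort and subject, but does not create one.

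**4. Can it be recovered from SAP section 9?** Sections 9.1 to 9.7 contain no medication output. Other safety data keep their timing: for example, SAP 9.3 says that "dipstick urinalysis and microscopic laboratory results will be listed by visit per subject". Adverse event summaries in SAP 9.1 are restricted to treatment-emergent events, with a window from first dose to 30 days after last dose, or to the day before subsequent anti-tumor therapy if that comes first. The pooled medication table starts earlier, so it does not line up with those summaries.

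**5. A boundary case.** Protocol 6.8.3 requires an antipyretic and an antihistamine 30 minutes to 2 hours before the first TJ004309 infusion. Protocol 6.4 gives atezolizumab after TJ004309, so that infusion is the first study drug dose. By clock time this premedication precedes the concomitant window, although it is part of the study regimen. A split table therefore needs a stated rule for it.

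**The case against.** The strongest reply is that the protocol promises no particular medication table. Section 9.2.5 and the synopsis name concomitant medication use as an input to the safety assessment, but neither asks for a separate count. The synopsis paragraph on safety presentation covers adverse events, vital signs, ECG, ECOG status, laboratory tests and physical examination, not medications. This stands: the pooled table does not break a commitment to a specific output.

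A reader might also infer that concomitant medications have been left out, because SAP section 9 has no heading for them. The documents do not support that. Medications are reported in section 6, pooled. Nor is there a fair contrast with the endpoints and analyses that SAP sections 8 and 10 to 12 openly set aside, since medications are not set aside.

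Third, the SAP is written in accordance with the protocol, which defines both windows, and table shells are not among the documents. A shell might split the table. That limits certainty about the final output, but the SAP as written states a pooling rule, and nothing in it restores the split.

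Finally, the report is abbreviated and Part 2 was not initiated. This bears on how much the point matters. It does not explain producing a medication table that cannot separate the two periods.

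**Conclusion.** The point holds as a minor one. As SAP 6.9 is written, on-study medication use cannot be separated from pre-treatment use in any stated output, and each pooled count only bounds on-study use from above.

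The documents give no patient-level size for this. They contain no medication counts, so the number of patients who would be misclassified is unknown, and even the appearance of a corticosteroid row depends on at least one recorded use. A reader might infer that steroid exposure will be misstated by some definite amount, or that the efficacy reading is affected. Neither follows: the effect is descriptive, and objective response rate, the Cohort 1 futility rule and the Part 2 decision do not use these data.

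The conclusion rests on reading SAP 6.9 as one pooled summary, and on no unpublished shell or listing supplying the split. SAP 6.10 pools procedures in the same way, but the protocol does not name procedures as a safety measure, so the point is confined to 6.9.

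**What to change.** In SAP 6.9, replace the pooled table with two, using the protocol 6.8 windows:
- **Prior:** use in the 28 days before first dose.
- **Concomitant:** use from first dose through 30 days after last dose.
- **Ongoing at first dose:** count in both tables.
- **Cycle 1 Day 1 premedication:** count as concomitant. State this as an explicit SAP convention, because a strict clock-time reading of protocol 6.8 would place it under prior.
- **Systemic corticosteroids:** make them identifiable by route in the concomitant table, so that topical, inhaled and systemic use are not merged.

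The cost is one extra table. Protocol 6.8 already distinguishes the two kinds of medication, and 6.8.2 has the CRF record dose, route, indication and duration, so no new data collection should be needed. This assumes that the recorded dates or duration show whether a drug was ongoing at first dose. The protocol names duration but not start and stop dates, and SAP 6.9 describes a single shared CRF page, so this should be confirmed before the table is specified.

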6.10 PRIOR AND CONCOMITANT PROCEDURES

All procedures collected on the CRF page ‘Prior and Concomitant Procedures’ will be coded to SOC and PT using MedDRA version 25.1. The number and percentage of subjects who had at least one prior or concomitant procedures will be summarized by SOC and PT. A subject who had multiple prior or concomitant procedures in a SOC/PT category will only be counted once for that category.

6.11 SUBSEQUENT SYSTEMIC THERAPY

Subsequent systemic therapies will be listed by subject.

6.12 SUBSEQUENT RADIOTHERAPY

Subsequent radiotherapies will be listed by subject.

6.13 SUBSEQUENT SURGERY/PROCEDURE

Subsequent surgeries/procedures will be listed by subject.

7 STUDY DRUG EXPOSURE AND ADMINISTRATION

The safety analysis set will be used for the summary tables and data listings in this section.

A summary of study drug exposure will be presented for TJ004309 and atezolizumab, respectively, and will include:

- Treatment duration (months).

- Total cumulative dose (mg) infused, calculated as the sum of the actual doses infused.
- Number of treatment cycles initiated.

A treatment cycle is defined as a cycle in which the subject received any amount of study drug. Each cycle will be 21 days in duration. If a cycle is prolonged due to toxicity, it should still be counted as one cycle.

The treatment duration (months) for a subject on a study drug is calculated as [min(last dose date + 20, date of study completion (or discontinuation), date of death) - first dose date + 1]/30.4375.

A summary of infusion modifications for TJ004309 will be presented where the number and percentage of subjects are calculated for the following categories:

- Number of interrupted infusions (1, 2, ≥ 3)
- Number of infusions where infusion rate was decreased (1, 2, ≥ 3)
- Number of partial infusions (1, 2, ≥ 3)

The study drug exposure and infusion modifications for each study drug will be listed by subject. The infusion administration information for each study drug per study visit will also be listed by subject.

8 EFFICACY ANALYSIS

The efficacy evaluable analysis set will be used for the efficacy summary.

The anti-tumor efficacy of the combination of TJ004309 and atezolizumab will be summarized by best of response (BOR) and objective response rate (ORR) assessed by the Response Evaluation Criteria in Solid Tumors (RECIST 1.1) and immune RECIST (iRECIST) guidelines. All tumor response data (including unscheduled tumor assessments) will be used in the efficacy analysis.

Efficacy endpoints such as duration of response (DOR), progression-free survival (PFS) and overall survival (OS) will not be reported due to the abbreviated nature of the CSR to be produced.

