- t) Dipstick is acceptable. Microscopic analyses if dipstick is abnormal. No need to repeat on Cycle 1 Day 1 if screening assessment performed within 72 hours prior to that date. If  $\geq 2+$  protein on urine dipstick, then collect spot urine sample to calculate urine protein to creatinine ratio.
- u) Tumor assessments will be performed at Screening, Cycle 4 Day 1, then every 9 weeks for 1 year following the first dose of study drug, and every 12 weeks for the second year. Scans within 28 days of Cycle 1 Day 1, prior to signing the ICF, can be used as the screening scan. On-treatment scans can be obtained  $\pm 7$  days. The same modality (CT, PET/CT or MRI) should be used throughout the study for a given patient. Collection of images will be obtained for retrospective analysis. Central review of scans may be performed during the study.

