**Non-target lesions**

All other lesions (or sites of disease) including pathological lymph nodes (with short axis  $\geq 10$  mm and  $< 15$  mm) should be identified as non-target lesions and should also be recorded at baseline. Measurements are not required and these lesions should be followed as ‘present,’ ‘absent,’ or in rare cases ‘unequivocal progression’ (more details to follow). In addition, it is possible to record multiple non-target lesions involving the same organ as a single item on the Case Report Form (e.g., ‘multiple enlarged pelvic lymph nodes’ or ‘multiple liver metastases’).

**Response Criteria:** The BOR is the best response recorded from the start of the study treatment until the end of treatment. The subject’s BOR assignment will depend on the findings of both target and non-target disease and will also take into consideration the appearance of new lesions.

**Complete Response (CR):** Disappearance of all target lesions. Any pathological lymph nodes (whether target or non-target) must have decreased in size to have a short axis of  $< 10$  mm.

**Partial Response (PR):** At least a 30% decrease in the sum of diameters of target lesions taking as reference the baseline sum diameters.

**Stable Disease (SD):** Neither sufficient shrinkage to qualify for PR nor sufficient increase to qualify for progressive disease (PD), taking as reference the smallest sum diameters while on study.

**Non-CR/Non-PD:** Persistence of one or more non-target lesion(s) and/or maintenance of tumor marker level above the normal limits.

**Progressive Disease (PD):** At least a 20% increase in the sum of diameters of target lesions, taking as reference the smallest sum on study (this includes the baseline sum if that is the smallest on study). In addition to the relative increase of 20%, the sum must also demonstrate an absolute increase of at least 5 mm. For non-target lesions, unequivocal progression (see comments below) of existing lesions represents PD. Note: the appearance of one or more new lesions is also considered progression.

Lymph nodes identified as target lesions should always have the actual short axis measurement recorded (measured in the same anatomical plane as the baseline examination), even if the nodes regress to below 10 mm on study. This means that when lymph nodes are included as target lesions, the 'sum' of lesions may not be zero even if CR criteria are met, since a normal lymph node is defined as having a short axis of <10 mm.

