### Stable disease (SD) duration

Stable disease is measured from the start of the treatment until the criteria for progression are met, taking as reference the smallest sum on study (if the baseline sum is the smallest, this is the reference for calculation of PD).

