8.1 BEST OVERALL RESPONSE (BOR) AND OBJECTIVE RESPONSE RATE (ORR) PER RECIST v1.1

Responses to the study treatment are categorized per RECIST 1.1 as the following (from the best to the worst): complete response (CR), partial response (PR), stable disease (SD), progressive disease (PD) and not evaluable (NE).

Per RECIST 1.1, the best overall response (BOR) for a subject is the best response of CR, PR, SD, PD and NE observed from the first dose of study drug until PD or the end of

treatment, whichever occurs earlier. The objective response rate (ORR) is the proportion of subjects whose BOR is either CR or PR.

8.2 iBOR AND iORR PER iRECIST

iRECIST is based on RECIST 1.1 but adapted to account for the unique tumor response seen with immunotherapeutic drugs. iRECIST introduces new criteria of unconfirmed progressive disease (iUPD) and confirmed progressive disease (iCPD) to prevent the discontinuation of study treatment in cases of pseudoprogression. Immune responses assigned by the iRECIST criteria are (from the best to the worst): complete response (iCR), partial response (iPR), stable disease (iSD), unconfirmed progressive disease (iUPD), confirmed progressive disease (iCPD) and not evaluable (NE).

There is no distinct iRECIST assessment until radiographic disease progression based on RECIST 1.1. For participants who show evidence of radiological PD by RECIST 1.1 as determined by the Investigator, the Investigator will decide whether to continue a participant on study treatment until repeat tumor imaging is obtained for confirmation of PD by iRECIST.

Per iRECIST, the best overall response (iBOR) for a subject is the best response of iCR, iPR, iSD, iUPD, iCPD and NE observed from the first dose of study drug until iCPD or the end of treatment, whichever occurs earlier. The objective response rate (iORR) is the proportion of subjects whose iBOR is either iCR or iPR.

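### SAP 8.1 and 8.2 set no minimum time for stable disease, so one early unscheduled scan can decide whether a subject who progresses at the first planned scan is tabulated as SD or PD

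*SAP*

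**What the plan says.** SAP 8 (Efficacy Analysis) includes every assessment: "All tumor response data (including unscheduled tumor assessments) will be used in the efficacy analysis". SAP 8.1 says that "the best overall response (BOR) for a subject is the best response of CR, PR, SD, PD and NE observed from the first dose". Its search stops at progression or when treatment ends, whichever comes first, and it orders the categories CR, PR, SD, PD, NE from best to worst. SAP 8.2 has the same structure for iBOR, with iSD above iUPD and iUPD above iCPD. SAP 4.4 applies no analysis visit windows, so an early scan is neither assigned to a planned visit nor set aside.

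Protocol Appendix 1 adds no time condition. On best response it says "The BOR is the best response recorded from the start of the study treatment until the end of treatment". It defines SD by change in tumor size alone. On duration it says "Stable disease is measured from the start of the treatment until the criteria for progression are met", which fixes how SD is timed but not how long it must last before it counts. The appendix table comparing RECIST 1.1 with iRECIST says that SD needs no confirmation under either.

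The scan schedule is in footnote u to protocol Table 2: "Tumor assessments will be performed at Screening, Cycle 4 Day 1, then every 9 weeks for 1 year following the first dose". On-treatment scans may be done 7 days either side. Table 2 gives visits from Cycle 2 onward a window of 2 days either side.

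SAP 8.3 reports the number and percentage of subjects in each BOR and iBOR category, and gives Clopper-Pearson intervals for ORR and iORR.

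**The concern.** A best-response category should depend on the course of the disease and on a common assessment schedule, not on whether someone ordered an extra scan. Under the rule as written, a single unscheduled scan a few weeks after first dose, showing neither response nor progression, fixes SD as the worst best response the subject can receive. Progression at the first planned scan cannot undo it. If no later scan is done, the early scan alone yields SD, although the subject was never assessed at the planned time.

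What is at stake is the SD row, with the PD and NE rows, in the two best-response tables. SAP 8 drops DOR, PFS and OS from the abbreviated report, and SAP 8.3 does not compute the disease control rate, although SAP 2.2.2 lists it as a secondary endpoint. The BOR and iBOR tables are therefore the only efficacy summaries from which a reader could judge disease control.

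**Working it through.** The documents state no figure on this point, so there is none to reproduce. The check applies the SAP 8.1 rule to short scan histories.

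**Inputs**
- Category order and stopping point: SAP 8.1 (CR > PR > SD > PD > NE, up to PD or end of treatment).
- All scans count: SAP 8.
- Cycle length 21 days: SAP 3.1.
- First planned scan at Cycle 4 Day 1, scan window 7 days either side: protocol Table 2, footnote u.
- Visit window 2 days either side from Cycle 2: protocol Table 2.
- Up to 30 subjects per cohort: SAP 3.1.
- Day of the unscheduled scan: Day 30, assumed for illustration.

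**Timing**
- Cycle 4 Day 1 = 3 × 21 + 1 = Day 64.
- Scan window around nominal Day 64: 64 − 7 = Day 57 to 64 + 7 = Day 71.
- If the scan window is tied to the actual visit and that visit is 2 days early: 64 − 2 − 7 = Day 55.
- If the 2 days accumulate over three cycles: 64 − 6 − 7 = Day 51.

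**Rule applied**

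| Scan history | SAP 8.1 as written | SD only from Day 57 | Proposed rule |
|---|---|---|---|
| A: PD at Day 64 | PD | PD | PD |
| B: unscheduled SD at Day 30, PD at Day 64 | SD | PD | PD |
| C: unscheduled SD at Day 30, no later scan | SD | NE | NE |
| D: unscheduled PD at Day 30 | PD | PD | PD |
| E: SD at the Cycle 4 Day 1 scan, done on Day 55; PD at the next scan | SD | PD | SD |

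A and B have the same finding at the first planned scan but different best responses. D shows that an early scan which finds progression causes no problem. E shows why a bare Day 57 cut-off is not enough: it would reject SD from a scan that the windows allow.

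**Size per affected subject**

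The shift is 100/n percentage points, where n is the size of the efficacy evaluable set in the table:
- n = 15: 100/15 = 6.7 points
- n = 30: 100/30 = 3.3 points
- n = 60 (both cohorts full, overall column): 100/60 = 1.7 points

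The number of affected subjects is not given. For an assumed 0 to 3 in a cohort of 30, the SD row shifts by 0 to 3 × 3.3 = 10 points.

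**Response rates**

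ORR counts CR and PR, and iORR counts iCR and iPR. Moving a subject among SD, PD and NE changes neither the numerator nor membership of the analysis set, so both rates and their intervals stay the same. The Cohort 1 futility rule counts responses and is also unaffected.

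**The case against.** The strongest reply is that nothing of consequence moves. The primary endpoint is ORR, only ORR and iORR carry intervals, and SAP 4.1 records that Part 2 was not initiated because too few responses were seen. No decision depends on the SD row. This stands, and it limits the point to a descriptive table.

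Second, the SAP departs from nothing in the protocol. Appendix 1 has no minimum SD time either, and no scan is planned before Cycle 4 Day 1. This also stands: the fault is a gap common to both documents, not a contradiction. The reference to RECIST 1.1 in SAP 8.1 does not close it, because the criteria set out in Appendix 1 give a programmer no interval to apply.

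Third, a reader might infer that early unscheduled scans are prompted by symptoms, so that the rule systematically turns early failures into SD and overstates disease control. The documents do not support that. They do not say why unscheduled scans are done or how often. A symptom-prompted scan that shows progression gives PD (history D). Misclassification needs an early scan without progression, followed by PD or by no further evaluable scan. The disease control rate that would be overstated is also not among the SAP 8.3 outputs.

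Fourth, a fixed Day 57 threshold could reject a scan done on schedule (history E). This is correct, and the proposed wording allows for it.

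**Conclusion.** The point holds in a limited form. As written, SAP 8, 8.1 and 8.2 let an unscheduled scan at any time after first dose establish SD or iSD as best response. Two subjects who both progress at Cycle 4 Day 1 can then be tabulated differently solely because one had an extra scan. The consequence is confined to the SD/PD/NE split, and its iRECIST counterpart, in the BOR and iBOR tables.

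The shift is 1/n per affected subject, or 3.3 points at n = 30. That figure assumes a full cohort in the efficacy evaluable set; a smaller set makes each subject count for more. How many subjects are affected cannot be determined from the documents. If no scan before the first planned one showed SD, the tables do not change. No claim is made that the SD percentage is in fact inflated, or that the primary result is biased. The correction is worth making because the rule gives an arbitrary result in a reported table and is easy to repair.

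**What to change.** Add to SAP 8.1 and 8.2:

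- SD or iSD counts as best response only if it comes from the scheduled Cycle 4 Day 1 assessment, including one done early within the permitted visit and scan windows, or from any scan on or after Day 57.
- SD seen only earlier and followed by PD gives BOR = PD. Under iRECIST, the subject takes the better of the progression categories then observed by the SAP 8.2 ranking (iUPD, or iCPD if confirmed).
- SD or iSD seen only earlier, with no later evaluable scan, gives NE.
- The rules for CR and PR, and for iCR and iPR, are unchanged. Unscheduled scans continue to count for response and for progression.

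The cost is a few lines of SAP text and one extra condition in the program, which must recognize the scheduled Cycle 4 Day 1 scan as well as the date. The reported SD percentage may come out slightly lower. Scan timing and patient management do not change.
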